## **1. BACKGROUND/RATIONALE**

Psoriasis is a prevalent global skin disease (1). Psoriasis is not simply an inflammatory disease of the skin but also a systemic inflammatory condition that carries a higher risk for cardiovascular disease and other systemic comorbidities. Certain inflammatory markers are known to be elevated in the serum of patients with psoriasis. Some of these markers may correlate with severity and extent of skin lesions (i.e. PASI score), while others may not (2). Therapies that decrease the inflammation present in the skin could lead to a systemic decrease in inflammatory mediators, thereby lowering the risk for developing comorbidities. UVB phototherapy has been employed in the treatment of psoriasis for decades. The UVB wavelengths most effective for psoriasis (i.e. action spectrum) falls within 308-313 nm. Narrowband UVB (311 nm) is the most popular phototherapeutic modality for full body treatment, in which unaffected normal skin is also exposed to UV light. Lesion targeted NUVB became feasible upon the introduction of 308 nm excimer lasers. This strategy not only spared normal skin from unnecessary UV, but also allowed for higher doses of UV to be delivered on lesional skin, within a reasonable amount of time. Currently, excimer laser treatment of psoriasis is an FDA-approved therapy. Whereas changes in serum resistin have been demonstrated after NUVB (3), there is no data regarding targeted UVB excimer laser treatments and serum inflammatory markers.

Hyperpigmentation is a common adverse effect reported after targeted UVB phototherapy (4,5). In our clinical experience, the Photomedex Xtrac® Velocity Excimer Laser has resulted in minimal to no hyperpigmentation after psoriasis plaque treatment. Furthermore, there is a lack of research objectively measuring hyperpigmentation and erythema after excimer laser treatment.

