## **2. STUDY OBJECTIVES/HYPOTHESIS**

The overall aims for this study are to determine whether UVB excimer laser treatment of psoriasis affects serum inflammatory markers, and to assess hyperpigmentation and erythema with excimer laser treatment.

We hypothesize that treatment of psoriasis with UVB delivered via 308 nm excimer laser will decrease the levels of serum inflammatory markers. We hypothesize that treatment will decrease plaque erythema and will result in minimal hyperpigmentation

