**University Hospitals Case Medical Center**  
**Department of Dermatology**  
**Protocol**

**Protocol Title:** Effects of UVB Excimer Laser on Serum Inflammatory Markers in Patients with Psoriasis

**Principal Investigator:** [name], NP

**Co-Principal Investigator:** [name]

**3.2.6 Chromameter Assessment:** Treated plaques will be evaluated using a chromameter as an objective measure of hyperpigmentation and erythema at Screening Visit, Visit 8, Visit 16, Visit 23 Final/Early Termination Visit, and, if applicable, the 3 month follow-up visit. The chromameter uses the L\*a\*b\* color system. L\* measures skin reflectance or lightness, a\* measures red to green color saturation, b\* measures yellow to blue color saturation. Hyperpigmentation of treated plaques will be assessed via L\*. L\* values of treated plaques will be compared to L\* values of normal, untreated skin. Erythema of treated plaques will be assessed via a\*. a\* values of treated plaques will be compared to a\* values of normal, untreated skin. These values will also be compared from visit to visit.

**3.2.7 Limited Medical Exam:** Medical and Dermatological history, demographic information, concomitant medications, vital signs, height, weight, and BMI will be collected during Visit 1/Screening Visit.

**3.2.8 Blood Draw:** Blood will be drawn at Visit 1/Screening Visit and at Visit 23 Final/Early Termination Visit by venipuncture and will be evaluated for:

- Serum Inflammatory Markers: (e.g. Levels of CRP, resistin, MPO and S100, etc) as quantified via ELISA kits [ $\sim$ 10mL blood].
- Pro-Inflammatory Monocytes (optional): Populations of monocytes will be characterized in the blood and via flow cytometry analysis [ $\sim$ 60mL blood].

**3.2.9 Questionnaires:** Subjects will be asked to complete two questionnaires.

**3.2.5.1 Patient Satisfaction Survey:** Patients will be asked to complete a survey, scoring their satisfaction with the treatment at Visit 23 Final/Early Termination Visit.

**3.2.5.2 Nutrition Questionnaire:** Patients will be asked to complete a survey about their nutritional habits at Visit 1/Screening Visit.

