### **3.3 STUDY VISITS**

#### **3.3.1 Visit 1: Screening Visit (estimated time: ~ 90 minutes)**

- Subjects will review the Institutional Review Board (IRB) approved Informed Consent Form (ICF) with the study staff. After all study procedures have been discussed and all questions have been answered, subjects will affirm participation by signing and dating the consent form.
- Inclusion/exclusion criteria will be reviewed and subject eligibility confirmed.
- Study staff will review concomitant medications and procedures with each subject.
- Medical and Dermatological History information will be collected.
- Vital signs, height, weight and BMI will be collected and recorded.
- Subjects will have their psoriasis clinically evaluated through PASI scoring and PGA.
- A chromameter will be used to evaluate pigmentation before treatment.
- Subjects will have plaque/body photographs taken
- Subjects will undergo a Sunburn MED Test or Visual MED Test.
- Subjects will complete a dietary/nutrition questionnaire.
- Subjects will undergo a pre-treatment blood draw.
- An optional, pre-treatment punch biopsy may be taken from a psoriasis lesion.

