#### **3.3.3 Treatment Visits (Visits 3-22) (estimated time: up to 1 hour):**

***\*Patients will undergo Treatment twice a week until they reach a PASI 75 improvement, or until they reach the maximum of 20 total treatments\****

- Study staff will review concomitant medications, any AEs since the previous visit, and procedures with each subject.
- Subjects will have their psoriasis clinically evaluated through PASI scoring and PGA every four weeks during Visit 8 and Visit 16.
- During Visit 8 and Visit 16, treated plaques will be evaluated using a chromameter to measure hyperpigmentation and erythema that may be caused by the laser.
- Subjects will have plaque/body photographs throughout this study.
- Subjects will undergo standard clinical treatment with an Excimer Laser.

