**University Hospitals Case Medical Center**  
**Department of Dermatology**  
**Protocol**

**Protocol Title:** Effects of UVB Excimer Laser on Serum Inflammatory Markers in Patients with Psoriasis

**Principal Investigator:** [name], NP

**Co-Principal Investigator:** [name]

**3.3.4 Visit 23: Final Visit/Early Termination Visit [2 days-2 weeks after last treatment]  
(estimated time: up to 1 hour )**

- Subjects will have their psoriasis clinically evaluated through PASI scoring and PGA.
- Treated plaques will be evaluated using a chromameter to measure hyperpigmentation and erythema that may be caused by the laser.
- Subjects may have plaque/body photographs taken.
- Subjects will undergo a post-treatment blood draw.
- Optional, post-treatment punch biopsies may be taken from a psoriasis lesion.
- Subjects will fill out the Patient Satisfaction Survey.

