## **14. DATA ANALYSIS PLAN**

- 14.1 Clinical Outcome:** Clinical evaluation through PASI scoring and PGA will be performed, supported by photographic documentation. Percent change in PASI and number of treatments to obtain PASI 75 improvement will be calculated for each patient and results summarized as descriptive statistics using means and standard deviations.
- 14.2 Serum inflammatory markers:** Levels of inflammatory markers in the serum e.g. CRP, resistin, MPO and S100. will be quantified pre and post treatment via ELISA kits and correlated with PASI score, total number of treatments received, BMI and nutrition data, using multivariate regression analyses.
- 14.3 Optional flow cytometry analysis:** Populations of monocytes will be characterized in the blood and response to excimer laser expressed in improvement in PASI scores will be correlated with levels of specific pro-inflammatory monocytes using Pearson correlation coefficient. Level of pro-inflammatory monocytes will also be correlated with levels of CRP, resistin, MPO, S100.
- 14.4 Chromameter Assessment:** Hyperpigmentation of treated plaques will be assessed via  $L^*$ .  $L^*$  values of treated plaques will be compared to  $L^*$  values of normal, untreated skin. Erythema of treated plaques will be assessed via  $a^*$ .  $a^*$  values of treated plaques will be compared to  $a^*$  values of normal, untreated skin. These values will also be compared from visit to visit. They will also be correlated with response to treatment.
- 14.5 Patient Satisfaction Questionnaire:** Each item in the survey will be scored from 1-5. Scores will be summarized and descriptive statistics will be used. Satisfaction scores will also be correlated with PASI improvement.

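### Does Section 14.4 need to name one L\* contrast, one visit and a limit before the hypothesis of minimal hyperpigmentation can be addressed?

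*Combined protocol and SAP*

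**What the plan says.** Assessing hyperpigmentation is one of the study's aims. Section 1 notes that "there is a lack of research objectively measuring hyperpigmentation and erythema after excimer laser treatment", and Section 2 states: "We hypothesize that treatment will decrease plaque erythema and will result in minimal hyperpigmentation".

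Section 3.2.6 explains that L\* "measures skin reflectance or lightness". Under Section 14.4, "Hyperpigmentation of treated plaques will be assessed via" L\*, and the next sentence sets treated plaques against normal, untreated skin. After the parallel sentences on a\* for erythema comes the second comparison: "These values will also be compared from visit to visit". Section 14.4 then adds a correlation of the readings with treatment response.

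Section 3.2.6 and the schedule in Section 3.4 place chromameter readings at five time points: screening, Visits 8, 16 and 23, and the optional 3-month visit. On the screening reading, Section 3.3.1 says: "A chromameter will be used to evaluate pigmentation before treatment". For Visits 8 and 16, Section 3.3.3 says "treated plaques will be evaluated using a chromameter to measure hyperpigmentation and erythema that may be caused by the laser". Visit 23 falls "2 days-2 weeks after last treatment" (Section 3.3.4).

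Section 3 plans 24-27 patients. The documents give no alpha, power, SD or margin for L\*.

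**The concern.** The plan has a directional hypothesis, two L\* contrasts and no rule linking them. No L\* difference is named as minimal, so no result is defined that would contradict the hypothesis. An analyst who had seen the data could feature whichever contrast looked more favourable.

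The two contrasts are also not interchangeable. The screening reading is of an untreated psoriatic plaque. Treatment runs to PASI 75 or 20 treatments (Section 3.2.2), so the plaque is expected to change. L\* registers lightness from any cause, so a change from screening can reflect clearing as well as pigment. If active plaques are darker than normal skin, clearing could hide true darkening; if they are lighter, it could exaggerate it. At stake is the objective pigment result that Section 1 offers as part of the study's rationale.

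**Working it through.** The plan states no L\* figure, so there is nothing to reproduce. The check has three steps.

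**1. What the text commits to.** Sections 3.2.6 and 14.4 attach plaque versus normal skin directly to the statement about L\*, and bring in the visit comparison afterwards as an addition. The natural reading makes plaque versus normal skin the lead contrast. Both comparisons are stated as things that will be done, so reporting only one would depart from the plan. 'Visit to visit' also covers Visit 8 to 16 and 16 to 23, not only change from screening.

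**2. How the contrasts behave.** All inputs here are assumptions:
- E = L\* units by which the plaque is darker (+) or lighter (-) than normal skin at screening
- c = share of that gap cleared by Visit 23
- m = true darkening from pigment
- normal skin is unchanged and effects are additive

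The plaque-minus-normal gap at screening is -E. Then:
- Visit 23 difference = -E × (1 - c) - m
- change from screening = E × c - m
- change minus difference = E, for every c and m

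With m = 2:

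| E | c | Change from screening | Visit 23 difference |
|---|---|---|---|
| 5 | 0.25 | -0.75 | -5.75 |
| 5 | 0.5 | +0.5 | -4.5 |
| 5 | 0.75 | +1.75 | -3.25 |
| 5 | 1 | +3.0 | -2.0 |
| 1 | 0.75 | -1.25 | -2.25 |
| 0 | any | -2.0 | -2.0 |
| -3 | 0.75 | -4.25 | -1.25 |
| -3 | 0.25 | -2.75 | +0.25 |

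The correct answer in every row is -2.0. The error is E × c for the change and -E × (1 - c) for the Visit 23 difference. The latter is smaller in size only when c > 0.5, and vanishes only at c = 1. When c lies between 0 and 1, the two darkening estimates, m - E × c and m + E × (1 - c), bracket m. In the third row they are -1.75 and 3.25, on either side of 2.

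The documents do not give c. PASI 75 does not supply it: PASI is a whole-body composite of erythema, thickness, scaling and area (Section 3.2.4), and patients may stop at 20 treatments or terminate early without reaching it.

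**3. What a formal limit would require.** The 95% CI half-width for a paired mean is t(0.975, n - 1)/√n. That is 0.42 SD for n = 24 and 0.40 SD for n = 27. With an assumed SD of 2 to 4 units, it is 0.84 to 1.69 units at n = 24. For an 80% chance that the whole interval lies below a margin, the margin must exceed the true mean darkening by 0.60 SD (n = 24) or 0.56 SD (n = 27). The documents give no SD and no basis for a margin, and plan no repeat normal-skin readings from which to build one. Repeat readings would in any case measure repeatability, not what counts as minimal.

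**The case for a change.** The strongest case for a change is that hyperpigmentation is a stated aim with a directional hypothesis, so even a descriptive report needs a named contrast, a visit and an interval. The cost would be mainly wording. With 24-27 patients, a non-significant difference would not establish that pigmentation is minimal.

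Much of this stands. 'Minimal' is undefined throughout, no visit is named as decisive, and the body site of the normal-skin reading is not fixed. The visit lists in Sections 3.3.3 to 3.3.5 mention only treated plaques, although Section 3.2.6 sets out the normal-skin comparison alongside all five time points. A change from screening can contain clearing, whether it is taken on raw plaque L\* or on the plaque-minus-normal difference.

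What does not follow is that the remedy improves the plan. Naming plaque versus normal skin as the lead largely restates Section 14.4. Making Visit 23 decisive swaps contamination by clearing for contamination by residual lesion, and is worse if less than half the L\* gap clears. A test of a CI against a margin is confirmatory machinery for a one-group study whose analyses are descriptive or correlational. A single margin would also have to serve Fitzpatrick types I-VI. Reasonable statisticians would differ on whether to add it.

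**Conclusion.** No change follows. The plan leaves a definition unwritten, but it already collects and promises both contrasts, led by plaque versus normal skin. Together they bracket the true darkening under the stated assumptions, and their difference is the screening gap, which can be shown beside them. The planned correlation with response also bears on whether L\* moves with clearing. An analyst following Section 14.4 can present all of this and describe the pigment result without claiming that a prespecified limit was met.

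The size of the problem in this trial cannot be established. In the illustration, either contrast can be wrong in size or sign: +1.75 for the change from screening at E = 5, c = 0.75, and +0.25 for the Visit 23 difference at E = -3, c = 0.25, against a true -2.0 in both. These figures rest on assumed E, c and m, unchanged normal skin and additive effects. The documents give neither the size nor the direction of the clearing effect on L\*. The conclusion also assumes that both planned comparisons are reported.

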## **15. DATA AND SAFETY MONITORING PLAN**

### **15.1 Procedures for analysis and interpretation of data**

The PI or co-investigator holds meetings with the staff performing both the clinical and laboratory based assessments. These meetings occur on a minimum of a monthly basis, but

**University Hospitals Case Medical Center**  
**Department of Dermatology**  
**Protocol**

**Protocol Title:** Effects of UVB Excimer Laser on Serum Inflammatory Markers in Patients with Psoriasis

**Principal Investigator:** [name], NP

**Co-Principal Investigator:** [name]

often occur more frequently. These meetings are held for two primary functions: to discuss primary data and progress of the study. Data include both clinical observation and laboratory measurements. The secondary function of these meetings is to monitor clinical outcomes for potential adverse events associated with the study. The PI has put into place an action plan should adverse events occur during the course of the study. Adverse events that could be envisioned are outlined below:

- A. Responsible party for safety monitoring:** In addition to the PI, safety monitoring will also be performed by the designated medical study coordinator.
- B. Safety Monitoring Methods and Intervals:** Grading method and attribution for adverse event reporting AE will be graded according to the following 0-5 scale:

Score	Description
0	No Adverse Event or within normal limits or not clinically significant
1	Mild AE did not require treatment
2	Moderate AE resolved with treatment
3	Severe AE resulted in inability to carry on normal activities and required medical attention
4	Life threatening or disabling AE
5	Fatal AE

The PI will determine the relationship of AE's to the test procedure/agent/device as; not related, possibly related, or definitely related, using standard criteria for clinical trials.

- All reported AEs will be followed until the event resolves or stabilizes OR
- The event returns to baseline OR
- The event can be attributed to agents other than the study agent(s) OR
- The subject withdraws informed consent OR
- The subject is lost to follow up.

- C. Implementation of the data and safety monitoring plan:** Adverse event reports for this protocol will be submitted to the approved IRB. Adverse Event Report Form sent in a timely manner consistent with the approved IRB policy.

In addition, any serious adverse event (grade 3 or greater), with the exception of those reported in the protocol, must be reported to the sponsor by the investigator by telephone, fax or email within 24 hours. A notification form will then be sent to the sponsor by fax or email with acknowledgement of receipt within 48 hours of the event.

**University Hospitals Case Medical Center**  
**Department of Dermatology**  
**Protocol**

**Protocol Title:** Effects of UVB Excimer Laser on Serum Inflammatory Markers in Patients with Psoriasis

**Principal Investigator:** [name], NP

**Co-Principal Investigator:** [name]

The investigator will also inform the sponsor of adverse events and abnormal results of the analysis, which are defined as decisive for the evaluation of safety of persons taking part in biomedical research.

#### **16. PLANS FOR THE SUBJECTS AT THE END OF THE PROTOCOL**

At the last visit, patients will be advised that lesions that do not demonstrate improvement should be treated using other established therapies (e.g. topical steroids, retinoids, phototherapy, etc), and appropriate referrals will be made.

